4. TREATMENT PLAN

4.1 Agents Administration

Treatment will be administered on an outpatient basis. Reported adverse events and potential risks are described in **Section 6**. Appropriate dose modifications are described in **Section 5**.

No investigational or commercial agents or therapies other than those described below may be administered with the intent to treat the patient's malignancy.

The cycle length is 28 days. Treatment will consist of the combination of entinostat and nivolumab. A lead-in of entinostat 2 weeks prior to combination therapy at the dose of 5 mg/weekly, will be incorporated to help determine the effect of entinostat on immune-related parameters in tumor biopsies.

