4.2 Overall Study Design

The proposed study single institution, open-label, two-stage, phase 2 study evaluating the clinical activity and safety of entinostat plus nivolumab. We will enroll two cohorts of patients: unresectable or metastatic cholangiocarcinoma (Cohort 1) and unresectable or metastatic pancreatic adenocarcinoma (Cohort 2). The primary objective of the trial is to determine whether the combination of entinostat plus nivolumab yields a clinically compelling antitumor activity measured as objective response rate (ORR, assessed by RECIST 1.1).

Secondary endpoints include safety, progression-free survival (PFS), overall survival (OS), and immunologic correlates.

The study is planned with 27 evaluable subjects per histology based on a two-stage design that allows early termination for lack of efficacy.

Patients will receive a biopsy at baseline and on approximately day 14 of entinostat therapy and approximately after 6 weeks from Cycle 1 Day 1. An optional biopsy will be performed at the time of disease progression. After a fourteen-day lead in with entinostat monotherapy, patients will begin to concurrently receive entinostat 5 mg oral once a week plus nivolumab 240 mg every two weeks for approximately four months. After 4 months, nivolumab will be given at a dose of 480 mg fixed dose every 4 weeks (maintenance phase). Therapy may continue with entinostat 5 mg weekly plus nivolumab 480 mg every 4 weeks, until intolerance or progression. Nivolumab will be administered intravenously over a period of 30 minutes.

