5.1 Dose Criteria

Entinostat

Prior to administration of first dose of entinostat in each cycle, subject's organ function and treatment-related toxicities must have recovered to the following values:

- Absolute Neutrophil Count (ANC) \geq 1,000 x 106/L
- Platelets \geq 75,000 x 106/L
- Creatinine $\leq 1.5 \text{ x ULN OR} > 60 \text{ mL/min}$ for patient with creatinine levels $>1.5 \times$ institutional ULN.
- Non-hematologic toxicities ≤ Grade 2 as noted below for entinostat-related toxicity Nivolumab

Dosing of nivolumab will be delayed for any of the criteria listed below:

- Total bilirubin $\geq 1.5 \times ULN$ (for patients with diagnosed Gilbert's Syndrome, direct bilirubin should be within normal institutional limits).
- Aspartate aminotransferase (AST) and alanine aminotransferase (ALT) > 3 ×ULN **OR** ≥5 ×ULN for patients with liver metastases: NOTE appropriate evaluation for autoimmune transaminitis must be conducted
- Any ≥ Grade 2 non-skin, non-laboratory, drug-related adverse event, with the following exception:
- Grade 2 drug-related fatigue does not require a treatment delay.
- Grade 2 hypothyroidism or thyroiditis does not require a treatment delay

- Subjects with Grade 3 thyroiditis or hypopituitarism may be restarted with replacement hormones including thyroid hormone and physiologic doses of corticosteroids. NOTE: grading for hypophysitis with symptoms of headache, visual or neurologic changes or radiologic evidence of pituitary enlargement and other CNS events such as aseptic meningitis or encephalitis should be considered grade 3 events
- Any \geq Grade 3 skin, drug-related adverse event.
- Any \geq Grade 3 drug-related laboratory abnormality with the following exceptions:
- Grade 3 lymphopenia does not require dose delay
- Any Grade \geq 3 drug-related amylase or lipase abnormality that is not associated with symptoms or clinical manifestations of pancreatitis does not require dose delay.
- Isolated grade 3 or 4 electrolyte imbalances/abnormalities that are not associated

[figure not shown]

with clinical sequelae and are corrected with supplementation/appropriate management.

• Any adverse event, laboratory abnormality, or intercurrent illness which, in the judgment of the investigator, warrants delaying the dose of study medication

[figure not shown]

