10. STUDY CALENDAR

Notations/reminders for all calendars:

- Baselines assessments are to be conducted within 28 days of registration unless otherwise noted.
 □ Correlative blood and tissue sample participation is mandatory.
- Additional tests may be performed at the discretion of the treating investigator as per routine practice, or as otherwise clinically indicated.

The schedule should be followed as closely as is realistically possible; the schedule may be modified due to problems such as scheduling delays or conflicts (e.g., clinic closure, vacations, etc.) with the guidance of the IND Sponsor/designee, as appropriate, and will not be reportable as a deviation unless the endpoints of the study are affected.

- * Required \leq 7 days prior to the first dose of entinostat
- ** Required assessment windows during combination treatment for each cycle as noted (e.g., Days 1 and 15 is 3 days, weekly is ±1 day). Assessments on Days 1 and 15 should be completed/reviewed prior to planned nivolumab administration.

- *** After 4 months, nivolumab will be given at a dose of 480 mg fixed dose every 4 weeks (maintenance phase). Therapy may continue with entinostat 5 mg weekly plus nivolumab 480 mg every 4 weeks, until intolerance or progression.
- Patients will be assessed in clinic on D1 of every cycle, and will be contacted by phone weekly, on the weeks entinostat alone is self-administered at home.

Required \leq 14 days prior to the first dose of entinostat

NOTE: All timeframes noted after the lead-in phase refer to duration on combination treatment (e.g., first-restaging should occur after 8 weeks of initiation of combination treatment of entinostat and nivolumab.)

Table 10.1 Study Calendar

						cycle ** = 28 days)			Maintenance Phase		
Procedure	Baseline ¹	Lead-In Day -14*	Lead-In Day -7	Day 1 (±3 days)	Day 8 (±1 day)	Day 15 (±3 days)	Day 22 (±1 days)	Week 6 (+14 days)	Every 4 weeks, Beginning on week 16***	Every 8 weeks (±7 days) ²	EOT ³ 28 days After Last Dose (±7 days)
Informed Consent & Review of Eligibility Criteria	Х										
Medical History & Demographics	Х										
Physical Exam ⁴	X	X#		X				X	X		Х
Vital Signs, Height (only baseline), Weight	х	x		х				X	X		х
ECOG Performance Status	Х	х		х		X		X	Х		х
Oxygen Saturation	Х			х		X		Х	X		Х
Hematology Panel ⁵	Х	x		х		X		х	X ⁶		Х
Chemistry Panel ⁷	X	X		X		X		X	Х		Х
Coagulation Panel ⁸	X										
Thyroid Function ⁹	х			х		х		x	X		х
Hepatitis Serologies ¹⁰	х										

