Female subject of childbearing potential should have a negative urine or serum pregnancy test within 72 hours prior to receiving retreatment with study medication. NOTE: If a patient has a positive or indeterminate serum or urine pregnancy test, then an ultrasound must be done to rule out pregnancy to enroll on trial. A serum B-HCG value of <25 is considered a negative pregnancy test.

- ^{14.} Radiologic imaging of chest/abdomen/pelvis (CT preferred, abdominal/pelvis MRI will be performed for patients with CT contrast allergy) and any other imaging required per RECIST for the particular subject are required at baseline. A baseline bone scan or PET/CT could be required to assess bone disease in patients with suspected or known bone metastases. A baseline brain CT scan or MRI is requested in patients with suspected or known brain metastases. Repeat same modality(ies) in follow-up to follow known site(s) of disease, with other assessments as clinically indicated if one has not been done within the past 6 weeks.
- ^{15.} Entinostat is to be self-administered by the patient weekly.
- ^{16.} Patients will receive entinostat 5 mg oral once a week plus nivolumab 240 mg every two weeks for approximately four months. After 4 months (16 weeks), nivolumab will be given at a dose of 480 mg fixed dose every 4 weeks. Therapy may continue with entinostat 5 mg weekly plus nivolumab 480 mg every 4 weeks, until intolerance or progression.

- ^{17.} Blood for serum and plasma samples will be collected at baseline (D -14), after entinostat lead in (on approximately day 14 (D-1) of entinostat therapy), on week 6, prior to dosing on C2D15, and at the time of the EOT visit. Detailed instructions for blood collection, processing, and storage are provided in the Laboratory Manual.
- ^{18.} Mandatory fresh tissue samples will be collected at D-14 and after entinostat lead-in (on approximately day 14 (D-1) of entinostat therapy prior to dosing on C1D1) and on week 6, prior to dosing on C2D15. A ± 3 day window applies to both time points. All

J1798/Version 5.0/May 21, 2020

samples are collected pre-dose on treatment days). Approximately six (6) core biopsy specimens will be obtained with each biopsy as outlined; the cytopathology slide will also be retained and submitted, if performed (See Section 9.2.1) All

correlative blood/tissue studies should be performed on the same day.

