NOTE: If applicable, the daily dose of entinostat may occur prior to hematology/chemistry tests and these laboratory tests may be drawn at the same time as the correlative blood samples.

- ^{19.} A third mandatory biopsy will be performed at week 6 from Cycle 1, Day1. A window of +14 days applies to this time point
- ^{20.} An optional biopsy will be performed at the time of disease progression.
- ^{21.} Archival tumor specimens from previously collected samples will be obtained for correlative analysis, if available.
- ^{22.} Weekly assessments for toxicity/adverse events may occur by phone on days when entinostat alone is administered. Additionally, assessments are to continue for 30 days after the last dose of nivolumab (at intervals <21 days) or to resolution of drug-related AEs to \leq Grade 1, whichever occurs later. SAEs that occur within 100 days of the last treatment or before initiation of a new antineoplastic treatment should also be followed and recorded. These may occur by phone for subjects no longer being seen at the institution; however, an in-person clinic visit may be needed to confirm event resolution and/or to effectively evaluate possible immune-related events. Subjects must be told of follow-up requirements at study entry.
- ^{23.} Subjects who complete or discontinue from treatment because of progression disease will be followed (by phone or email) every three months (+/- 2 weeks) after completion of the EOT visit for up to 2 years or study closure to monitor overall survival. Information of other cancer therapies after discontinuation from the study treatment will also be collected.

For subjects who discontinue treatment for reasons other than tumor progression, will be contacted (by phone or email) every three months (+/- 2 weeks) after completion of the EOT for up to 2 years or study closure to monitor overall survival, and information

93

about disease status will be also collected if possible (i.e. radiological imaging and/or tumor markers) until documented tumor progression.

NOTE: For evaluation of PFS, all subjects who discontinue study drug administration prior to 6 months must have restaging scans/imaging within a 7 day window of the 6 month time point from the date of initiation of combination treatment

J1798/Version 5.0/May 21, 2020

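### A Study Calendar note lets entinostat be taken before the safety bloods, which conflicts with the Section 5.1 dosing criteria and with the pre-dose sampling rule for correlative blood

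*Combined protocol and SAP*

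**What the plan says.** The note sits in the Study Calendar between footnotes 18 and 19. It opens with a conditional (if applicable) and grants two permissions. The first concerns the order of dosing and testing: "the daily dose of entinostat may occur prior to hematology/chemistry tests". The second allows a single blood draw to serve both the safety tests and the correlative work.

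Other parts of the protocol bear on the same events:

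- **Section 5.1 (Dose Criteria).** Before the first entinostat dose of each cycle, "subject's organ function and treatment-related toxicities must have recovered to the following values". The entinostat list covers neutrophils, platelets, creatinine and non-hematologic toxicity.
- **Study Calendar notations.** "Assessments on Days 1 and 15 should be completed/reviewed prior to planned nivolumab administration". Entinostat is not named.
- **Footnote 18.** This covers the mandatory biopsies and adds that all "samples are collected pre-dose on treatment days". It also asks for correlative blood and tissue work on the same day.
- **Footnote 17.** The week 6 correlative blood is to be taken before the Cycle 2 Day 15 dose.
- **Entinostat frequency.** Section 4.1 gives the lead-in "at the dose of 5 mg/weekly". Section 4.2 gives "entinostat 5 mg oral once a week plus nivolumab 240 mg every two weeks for approximately four months". Footnote 15 says "Entinostat is to be self-administered by the patient weekly".

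**The concern.** Section 5.1 is mandatory and the note is permissive, and they point in opposite directions. Staff who follow the note can allow entinostat to be taken before the results that Section 5.1 relies on exist. The calendar's review-before-dosing notation does not settle the matter, because it protects nivolumab only.

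The second issue is interpretive. The lead-in is there to show what entinostat does to immune parameters (Section 4.1), and objectives 1.3.2 and 1.3.4 are about change after treatment. If some samples are drawn before that day's dose and others after it, a within-patient change can mix a short-term effect of the dose with the effect of interest, and the data would not show which samples were affected unless draw times were kept.

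The third issue is wording: the note calls a weekly drug's dose daily.

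**Working it through.** No design figure is involved, so the check sets the texts side by side, visit by visit. The entries come from the Study Calendar table and footnotes 15 to 19, and from Section 5.1.

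| Visit | Entinostat due | Safety bloods | Correlative blood | Section 5.1 entinostat check | Pre-dose sampling rule |
|---|---|---|---|---|---|
| Day -14 | yes | yes | yes | only if the lead-in counts as a cycle | yes (fn 18) |
| Cycle 1 Day 1 | yes | yes | yes in the table; fn 17 says about Day -1 | yes | yes (fn 18) |
| Day 1, later cycles | yes | yes | none under fn 17 | yes | not applicable |
| Week 6 (Cycle 2 Day 15) | yes | yes | yes | no, not the first dose of a cycle | yes (fn 17 and 18) |
| Days 8 and 22 | yes | no | no | no | not applicable |
| End of treatment | no | yes | yes | no | not applicable |

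Week 6 and Cycle 2 Day 15 are the same visit: with 28-day cycles, Cycle 2 Day 15 is day 28 + 15 = 43, which is 42 days, or 6 weeks, after Cycle 1 Day 1.

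**Step 1: dose against laboratory check.** The first permission conflicts with Section 5.1 wherever the fifth column says yes. The note follows the footnote on correlative sampling and mentions correlative blood, so its natural scope is the correlative-draw visits. Within that scope the overlap is Cycle 1 Day 1, with Day -14 added if the lead-in counts. Separately from Section 5.1, the calendar marks its Day -14 column as required within 7 days before the first entinostat dose, and that column includes hematology and chemistry. Nothing in the note states the limit to draw visits. Without it, the conflict extends to Day 1 of every cycle.

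**Step 2: dose against correlative draw.** Neither permission alone makes the correlative blood post-dose. Together they can: entinostat first, safety bloods afterwards, correlative blood in the same draw. That contradicts footnote 17 at week 6 and footnote 18 at Day -14 and Cycle 1 Day 1. Footnote 18 is mainly about tissue. If its rule were confined to tissue, the explicit blood rule in footnote 17 would still leave a conflict at week 6.

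**Step 3: frequency.** Sections 4.1 and 4.2, footnotes 15 and 16, the calendar columns (Days 1, 8, 15 and 22) and the four weekly rows of the Appendix C diary all give weekly dosing. Only the note says daily.

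**The case against.** The best defence is that the note is loose wording that does little harm in practice. A permissive *may* does not clearly waive the *must* in Section 5.1. The 3-day window around Day 1 lets staff draw bloods early and satisfy both texts. Patients are seen in clinic on Day 1 of every cycle, and home dosing is linked to the weeks when entinostat is given alone. Section 4.5.2.2 requires nivolumab infusion reactions to resolve before entinostat is given, which suggests that entinostat is not taken first on shared days. The post-lead-in sample is set at about Day -1, when no weekly dose is due, so a conflict arises there only if the draw moves to Day 1, although the calendar table does place it in that column. Sections 4.4.1 and 5.1.1 are not visible, and the Laboratory Manual is a separate document. Either may contain a timing rule.

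Most of this stands as a limit on scope and likely impact. It does not remove the contradiction: these texts make compliance possible, while the note still permits the opposite order and exempts no dose.

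Two stronger readings are not supported:

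- A reader might infer that the note introduces daily dosing. Every other schedule statement is weekly, the note concerns the order of blood tests, and the phrase most naturally means the dose due that day.
- A reader might infer from the adverse event rates in Section 6.1.1 that Section 5.1 would often be failed. The comparative rates there are given without grade and come from a lung cancer trial with erlotinib. Anemia is not among the listed entinostat criteria. The rates do not show how often a patient would miss a threshold on Day 1.

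**Conclusion.** The note contradicts Section 5.1 on the order of dosing and laboratory check and, when both its permissions are used, contradicts footnotes 17 and 18 on pre-dose sampling. Its reference to a daily dose is a lesser inconsistency of wording.

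The extent is bounded by visits. For the laboratory check it is Cycle 1 Day 1 at least, possibly Day -14, and Day 1 of every cycle on the unrestricted reading. For sampling it is Day -14, Cycle 1 Day 1 and week 6, or week 6 alone if footnote 18 covers tissue only. The documents do not allow an estimate of how many doses or samples would be affected, or of how large any acute effect on the biomarkers would be.

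The affected analyses are exploratory. The two-stage response-rate test (13 + 14 = 27 per cohort) does not depend on the note. The conclusion rests on the visible text and could soften if Section 4.4.1, Section 5.1.1 or the Laboratory Manual fixes the timing. This is an internal contradiction that should be fixed, not a flaw in the design.

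**What to change.** The sponsor should reconcile the note with Sections 4.1, 4.2 and 5.1, the Day 1 and 15 notation, and footnotes 15, 17 and 18. The protocol should then state which text governs the timing of entinostat relative to (a) the safety bloods and (b) the correlative draw, at which visits the note applies, and whether the lead-in counts as a cycle for Section 5.1. The reference to a daily dose should be reconciled with the weekly schedule in the same edit. Which order is right is for the sponsor to decide.

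The draw time of each correlative sample should be recorded. The Appendix C diary already captures the time of each entinostat dose, so the two together would show whether a sample was pre-dose or post-dose and allow the biomarker analysis to take account of it.

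The cost is a correction to one calendar note, a notice to staff at the single institution, and one added time field if draw time is not already collected.

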1.2 Secondary Objectives

- **1.2.1** To assess the safety and tolerability of entinostat plus nivolumab in patients with unresectable or metastatic cholangiocarcinoma and unresectable or metastatic pancreatic adenocarcinoma.
- **1.2.2** To assess the progression free survival (PFS) status of patients with unresectable or metastatic cholangiocarcinoma and unresectable or metastatic pancreatic adenocarcinoma treated with entinostat plus nivolumab at 6, 12 and 24 months.
- **1.2.3** To determine the overall survival (OS) status of subjects with unresectable or metastatic cholangiocarcinoma and unresectable or metastatic pancreatic adenocarcinoma treated with entinostat plus nivolumab.
- **1.2.4** To determine the overall survival (OS) status of subjects with unresectable or metastatic cholangiocarcinoma and unresectable or metastatic pancreatic adenocarcinoma treated with entinostat plus nivolumab at 6 months, at 1, 2 and 3 years.
- **1.2.5** To assess the duration of response among subjects who demonstrate an objective response to treatment with entinostat in combination with nivolumab.

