1.5 Secondary Endpoints

- **1.5.1** Adverse events as graded by NCI CTCAE active version.
- **1.5.2** Progression Free Survival (PFS) status at 6, 12 and 24 months.
- **1.5.3** Duration of Response (DOR).
- **1.5.4** Overall Survival (OS).
- **1.5.5** OS at 6 months, at 1, 2 and 3 years

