4.10 Duration of Follow Up

The Follow-Up Phase begins when the decision to discontinue a subject from study therapy is made (no further treatment with study therapy).

All subjects who discontinue investigational product should comply with protocol specified follow-up procedures as outlined in Section 10, Study Calendar.

A mandatory End of treatment (EOT) visit (+/- 7 days) should be performed 28 days after the last dose of study drug(s).

After completion of the EOT visit, subjects will be followed every 3 months for survival.

Subjects who are discontinued from the study treatment due to an unacceptable toxicity will be monitored for safety until the resolution of the AE to \leq grade 1 or stabilization or until initiation of a new therapy for their cancer, whichever occurs first.

SAEs will be collected and recorded throughout the study period, from the first dose of the investigational agent through 100 days (+ 14 days) after the last dose of study drug or end of the study (if thought to be related to study drug), or 30 days after the initiation of a new anticancer therapy, whichever is earlier.

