8.3.7 Overall survival

Overall survival is defined as the time from start of treatment until death due to any cause. If patient is still alive at the time of analysis, OS will be censored on the date of last known being alive.

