12.3.2 Analysis of Secondary Endpoints

- OS is defined as the duration of time from start of study treatment to time of death. For subjects lost to follow-up or whose vital status is unknown, every effort will be made to determine the date such subjects were last known to be alive. Such efforts may include phone calls, certified mail, and the checking of public records. Subjects who are alive or lost to follow-up as of the data analysis cutoff date will be right-censored. The censoring date will be determined from the date the subject was last known to be alive.
- PFS is defined as the time from cycle 1, day 1 of immunotherapy until first documented local progression or death due to any cause. Disease progression will be assessed using RECIST (version 1.1). Due to the expectation that some patients may experience delayed clinical responses to therapy, patients with disease progression by radiographic imaging or laboratory parameters during a 12-week evaluation period but without rapid clinical deterioration or significant change in performance status that requires additional immediate therapy may continue to receive treatment on study.

Subjects that meet the above criteria and continue on study therapy must discontinue treatment upon documentation of disease progression on the second scan. The date of progression will be backdated to the time of first RECIST criteria progression. Tumor assessments will be made using RECIST 1.1 and immune-related response criteria (irRC). Individuals will be censored at the date of the last scan for PFS if no event occurs.

Median time to event will be calculated and reported with confidence intervals.

Analysis of PFS will be restricted to evaluable individuals who complete at least one dose of entinostat, while the analysis of OS will be performed on all evaluable patients.

OS curves, OS medians with 95% CIs, and OS rates at 6, 12, 24 and 36 months with 95% CIs will be estimated using Kaplan-Meier methodology

PFS curves, PFS medians with 95% CIs, and PFS rates at 6, 12 and 24 months with 95% CIs will be estimated using Kaplan-Meier methodology.

• Duration of response (DOR) will be calculated for subjects who achieve a best overall response of CR or PR with entinostat in combination with nivolumab. For such subjects,

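### A 36-month overall survival rate is planned, but survival contact stops 2 years after end of treatment, so only patients treated for about 11 months or longer are scheduled for contact to month 36

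*Combined protocol and SAP*

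**What the plan says.** Three places commit to OS at 3 years. Section 1.2.4 sets the objective of OS in patients "treated with entinostat plus nivolumab at 6 months, at 1, 2 and 3 years". Section 1.5.5 lists "OS at 6 months, at 1, 2 and 3 years" as a secondary endpoint. Section 12.3.2 states that "OS rates at 6, 12, 24 and 36 months with 95% CIs will be estimated using Kaplan-Meier methodology". OS runs from the start of study treatment (Sections 8.3.7 and 12.3.2), and for a patient still alive, "OS will be censored on the date of last known being alive".

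Follow-up is described in two places:

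- Section 4.10 puts the EOT visit 28 days (±7) after the last dose and then says: "After completion of the EOT visit, subjects will be followed every 3 months for survival". It gives no end date, but it holds patients to "follow-up procedures as outlined in Section 10, Study Calendar".
- Footnote 23 of the Study Calendar gives the only stated length: contact "every three months (+/- 2 weeks) after completion of the EOT visit for up to 2 years or study closure to monitor overall survival". The same limit applies to patients who stop for reasons other than progression.

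Section 12.3.2 adds tracing for patients who are lost or whose status is not known: "Such efforts may include phone calls, certified mail, and the checking of public records".

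**The concern.** The follow-up limit counts from the end of treatment, while the landmark counts from its start. Treatment has no fixed length, so the time at which a living patient leaves scheduled contact depends on how long that patient was treated. For short-treated patients it comes well before month 36.

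From about month 25, living patients then leave the Kaplan-Meier risk set because of the schedule. Two things are at stake:

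- **Precision and existence of the estimate.** Few patients will be alive at month 36 in a cohort of 27, and the cap removes some of them. If the longest observed time in a cohort is a censoring before month 36, the 36-month rate cannot be estimated.
- **Bias.** Time on treatment ends mostly with progression or intolerance. If longer treatment goes with longer later survival, the patients left under observation are the better ones and the rate is too high. If it does not, the bias is close to zero.

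Footnote 23 also leaves open whether the 2 years or study closure governs, and it does not define closure.

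**Working it through.** The plan gives no figure of its own here; its computed figures concern the two-stage response design and do not enter.

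**Calendar arithmetic (document inputs only).** Landmark: 36 months = 1,096 days from first dose. Cap: 2 years = 730 days after EOT. EOT: 28 days after last dose (21 to 35 with the window).

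- Treatment time needed for scheduled contact to reach month 36: 1,096 − 730 − 28 = 338 days, or 11.1 months. With the EOT window: 1,096 − 730 − 35 = 331 days to 1,096 − 730 − 21 = 345 days.
- Patient who stops at 2 months: 61 + 28 + 730 = 819 days, or month 26.9. Stopping at 4, 6 or 9 months gives months 28.9, 30.9 and 33.9.
- Earliest cap: 28 + 730 = 758 days, or month 24.9.

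**Share treated long enough (assumption).** If treatment time is exponential, the share treated at least 11.08 months is 0.5^(11.08/median): 2%, 8%, 15% and 28% for medians of 2, 3, 4 and 6 months.

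**Effect on the estimate (simulation; treatment and survival times are assumptions).** Time on treatment is exponential, followed by exponential survival after stopping. Patients are censored at treatment end + 758 days, and no status is recovered by tracing. A long-term group of 0, 10 or 20% has medians of 14 months on treatment and 18 months afterwards. Bias comes from at least 2,000,000 simulated patients per scenario; the other figures are for cohorts of 27. A cohort counts as undefined when its largest observed time is a censoring before day 1,096. The low-end inputs reproduce the 5.9-month second-line pancreatic median cited in Section 2.1.1.

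Cells show 0/10/20% long-term group:

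| Medians, on treatment + after (months) | Median OS with no long-term group (months) | Censored before month 36, of 27 | Undefined, % of cohorts | True 36-month OS, % | Estimated, % |
|---|---|---|---|---|---|
| 1.7 + 3.3 | 5.9 | 0.1/0.6/1.0 | 12/12/5 | 0.11/5.44/10.77 | 0.11/5.83/11.26 |
| 2.5 + 6 | 9.9 | 1.4/1.7/2.0 | 48/16/5 | 2.67/7.77/12.89 | 2.69/9.17/14.47 |
| 4 + 8 | 14.2 | 2.7/2.8/3.0 | 22/8/3 | 8.68/13.13/17.60 | 8.89/14.20/19.03 |

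The bias is estimated minus true: 0.0/0.4/0.5 points, 0.0/1.4/1.6 points and 0.2/1.1/1.4 points by row.

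For the 2.5 + 6 row:

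- Of those alive at month 36, 84/43/34% have left scheduled contact.
- The mean number at risk at month 36 is 0.1/1.2/2.3, against 0.7/2.1/3.5 with contact to month 36.
- The binomial standard error, √(p(1−p)/27) at the true rate, is 3.1/5.2/6.4 points, larger than the bias.
- Of patients treated for less than 338 days, 91 to 94% still have known 36-month status, because most die before the cap.

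**The case against.** **The limit is ambiguous.** If study closure is the later of the two limits, or if Section 4.10 is read alone, contact could run past month 36 and the gap might not exist. The wording of footnote 23 sets a maximum, however, and Section 4.10 defers to the calendar, so the 2-year cap is the natural reading. A planned endpoint should not depend on the other one.

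**Tracing already covers it.** A patient past the cap with unknown status plausibly falls under the tracing provision in Section 12.3.2, and the figures above assume that it recovers nothing. This objection stands as to size. If tracing succeeds at random in 50% of such patients (an assumption), undefined cohorts in the 2.5 + 6 case fall from 48/16/5% to about 17/5/1%, and bias falls to about 0.0/0.5/0.7 points. At 80% they are about 6/2/0.4% and 0.0/0.2/0.2 points. Tracing still schedules no contact, and if deaths are found more readily than survivors it brings a bias of its own.

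**The landmark is weak anyway.** This also stands in part. In the 2.5 + 6 case without a long-term group, (1 − 0.0267)^27 = 48% of cohorts have nobody alive at month 36 even with full contact. In the low-end case the mean number at risk is 0.0/1.1/2.2 with the cap and 0.03/1.5/2.9 without it. That supports deleting the rate as a legitimate alternative, not keeping a rate that the schedule cannot support.

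**The bias rests on an undocumented subgroup.** Correct. The long-term group has no source in the documents, and without it the bias is 0.0 to 0.2 points.

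**Conclusion.** The concern holds. The mismatch follows from the documents alone: followed as written, the schedule stops contact with living patients before a named secondary landmark unless they were treated for about 338 days (331 to 345) or longer.

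The main consequence is a nearly empty risk set at month 36 and, in some cohorts, no estimate at all. Upward bias is secondary, conditional on treatment time predicting later survival, and below the standard error in every 2.5 + 6 scenario. All effect sizes rest on assumed treatment and survival times and on no recovery of status after the cap, so they are upper figures for those inputs if tracing recovers status without regard to outcome.

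The primary response rate and its decision rule are unaffected. OS at 6, 12 and 24 months is unaffected by the 2-year cap, since its earliest effect is at month 24.9. That is not guaranteed if an undefined study closure comes earlier. The landmark is descriptive and carries no test, so this is a change that should be made rather than a threat to the trial's main conclusion.

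**What to change.** Amend footnote 23, for every reason for stopping treatment, so that survival contact continues every 3 months until death or until the later of 2 years after EOT and 36 months from the first dose of study drug. Put the same end point in Section 4.10. Define study closure, and state that survival follow-up does not close before the last living patient reaches 36 months.

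If that is not wanted, delete the 36-month OS rate from Sections 1.2.4, 1.5.5 and 12.3.2.

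The first option costs at most (1,096 − 758)/91.3 = 3.7, so up to about 4, extra phone or email contacts per patient alive past about month 25. It also needs a protocol amendment with IRB approval, and possibly a later closure, but no extra visits or procedures. The second option also needs an amendment and gives up one descriptive figure.
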